15.0 Audio/Video Recording/Photography

For the needs assessment, we will not be recording participants in any form.

For the pilot study, we will audio and video recordings of zoom conversations between the parent coach and the participants. These recordings will be used for quality assurance and training purposes as well as to refine interactions between the parent coach and the participants. Data will be stored on FSM secure servers and not on the Zoom cloud. If a parent does not agree to being recorded, their sessions will not be recorded. Instead, the parent coach will take notes during the session to gather insight on how the session went.

16.0 Potential Benefits of this Research:

The needs assessment has multiple potential benefits for participants. First, it will allow participants to share their experiences and contribute to efforts to improve the fostering experience. Second, they will be able to contribute to research and inform practices to better support youth with special health care needs, particularly those with mental health needs.

The pilot study offers many potential benefits to participants. First, participants will be provided with the results of screenings that will give them insight into their youth's mental health needs. Second, they will be provided with personalized supports to find appropriate services and strategies to support their youth's needs. Third, foster parents will have opportunities to learn and practice skills and strategies with research staff that will allow them to better support their youth's mental health needs as well as their own emotional regulation. Fifth, foster parents will have access to a research-based curriculum regarding skills that can improve their ability to support their child's needs.

17.0 Potential Risks to Participants:

A potential risk for participants in both studies is that they might misconstrue our services to be comprehensive mental health services. However, our needs assessment is simply aimed at identifying needs to create recommendations to improve services while PROACTIVE Parent is only an educational program designed to support parents in

learning new skills, learning how to locate services for their child, and obtaining referrals to providers through a publicly accessible databases. Thus, while this program fills in gaps in traditional mental health services, it does not constitute comprehensive mental health treatment, a fact that will be consistently emphasized to participants throughout both parts of the study. We will explicitly include this in the consent form and check in with participants regularly to ensure that this is understood and that participants have access to complete services. In addition, parents might feel uncomfortable sharing personal information with research study staff. In order to mitigate this risk, we will emphasize that participants do not have to answer any question they do not want to or participate in any activity that makes them uncomfortable. If they continue to feel uncomfortable, they can choose to opt out of the remainder of the needs assessment or pilot study, depending on which they are enrolled in.

18.0 Provisions to Protect Participant Privacy and Data Confidentiality:

In terms of data storage, all data will be stored on secure Northwestern servers and only accessed by members of the research team. While the data will be stored with identifiers, since the research staff will need to contact participants, data will be de-identified when downloaded. When the data is being transferred from REDCap to the M drive, it will be downloaded on an FSM computer and immediately transferred to the appropriate M drive location. The data will be stored indefinitely on the M drive and on NU's REDCap server.

In terms of delivering the pilot intervention, all coach - participant check-ins will be held using confidential video-based software (e.g. Zoom) and will be conducted in a private setting where others not involved in the research project cannot hear the advocates' conversations with participants.

19.0 Data Monitoring Plan to Ensure the Safety of Participants:

Given that the pilot study will be working with caregivers of children with mental health issues and who are involved with the child welfare system, we will be monitoring the responses caregivers provide for potentially harmful situations during every interaction with research staff. Research staff will immediately make note of any potential issues during and after their interactions with participants, responding appropriately given the situation. Protocols have been developed for managing disclosures of child abuse or neglect as well as responding to indications of suicidality by the caregiver or youth. If research staff identify a need for more comprehensive mental health services, caregivers will be referred to the Service Provider IDentification & Exploration Resource (SPIDER) through DCFS to identify additional resources. In addition, the family's case worker will be notified of the increased need. If there is a direct risk to the child or caregiver's wellbeing, the proper authorities will be alerted. In addition, if the risk for or perpetration of abuse or neglect is suspected, research staff will immediately report relevant information to DCFS. If parents reveal any level of suicide risk, the youth's case worker

and, if necessary, emergency services will be immediately contacted. To promote full transparency, these potential breaches of confidentiality will be included in the consent form.

20.0 Long-term Data and Specimen Storage and Sharing:

All data collected from this study will be stored on FSM-approved drives. These include the REDCap server, as REDCap will be used to collect the data, and the FSM M-drive under the MHSPP folder. Because the participants are being hand-picked for this study and will be monitored over a period of time, data will have identifiers attached. However, only study staff will have access to identifiable data.

21.0 Qualifications of Research Team to Conduct the Research:

[name] is an Assistant Professor and Associate Director of the Mental Health Services and Policy Program at Northwestern University Feinberg School of Medicine. [name] research focuses on violence prevention, child welfare, parenting, and access to parenting and mental health promotion services for underserved children and families. [name] studies parenting interventions designed to promote positive parenting and prevent child physical abuse (CPA) through the use of innovative technologies.

Cover Page

Study: PROACTIVE Parent: PROviding Access To InnoVative & Evidence-Based Intervention

Date: 6/16/21

Statistical Plan

We plan to enroll 14 foster parents with 7 foster parents per condition.

For the primary outcomes: acceptability, usefulness, and feasibility we will conduct descriptive analyses separately for the post-session items and the post-intervention Customer Satisfaction Survey. We will sum relevant items on the post-session questionnaires (administered after each of the 10 sessions) and provide mean ratings for program Acceptability, Usefulness, and Feasibility. We will provide mean ratings for Acceptability, Usefulness, and Feasibility from the Customer Satisfaction Survey. We will also provide descriptive statistics for other aspects of Feasibility as described below.

For the primary Treatment vs. Control group analyses we will examine 2 (Group) x 2 (Time) repeated measures ANOVA, with repeated measures on the second factor (Time). For measures that include subscales we will use K (number of subscales) x 2 repeated measures MANOVA to assess for treatment effect on subscale scores. For the child outcome measures we will use 2 x 2 repeated measures MANOVA with each of the child outcome measures and/or subscale scores in one model, as the child outcomes may share some variance.

For the delayed treatment analyses, we will combine the treatment and the delayed treatment participants to examine a one-way repeated measures ANOVA examining the pre-post scores of each of the groups – essentially using T1 and T2 data for the original treatment group and the T3 and T4 data for the delayed treatment groups. We will use a one-way repeated measures MANOVA for the child outcomes.

Primary Outcomes. Primary Outcomes will be assessed with three types of measures. Post-session measures that assess session content and delivery at the end of each of the 10 sessions, post-intervention in a Customer Satisfaction Survey, and pre- and post-intervention with standardized measures.

Acceptability. Post-session acceptability assesses parent satisfaction with the session, what parents liked about the session, and what they would change about the session. Continuous items will be summed and analyzed using descriptive statistics. Qualitative analyses will be used to identify themes in open-ended questions. Items on the Customer Satisfaction Survey will be summed and analyzed using descriptive statistics. Qualitative analyses will be used to identify themes in open-ended questions.

Utility. Post-session utility assesses parent perspectives of the usefulness and relevance of the session. Continuous items will be summed and analyzed using descriptive statistics. Qualitative analyses will be used to identify themes in open-ended questions. Items on the Customer Satisfaction Survey will be summed and analyzed using descriptive statistics. Qualitative analyses will be used to identify themes in open-ended questions.

Feasibility. Post-session feasibility assesses parent perspectives of the timing and format of the session. Continuous items will be summed and analyzed using descriptive statistics. Qualitative analyses will be used to identify themes in open-ended questions. Items on the Customer Satisfaction Survey will be summed and analyzed using descriptive statistics. Qualitative analyses will be used to identify themes in open-ended questions. We will also assess feasibility by using descriptive statistics to assess the extent to which the parent coach was able to adhere

to the session format for each session, the percentage of parents who met eligibility criteria, enrolled in the study, and completed all study-related tasks.

Parent-Patient Activation Measure – Mental Health (P-PAM-MH). We will examine change in parent activation from baseline (T1) to post-treatment (T2, week 11) in the treatment condition relative to the control condition. Parent activation will be measured using the Parent-Patient Activation Measure- Mental Health. While the study is likely not powered to detect significant differences, our goal is to estimate effect sizes. We predict that parent scores in the treatment group, relative to the control group, will increase from baseline to Time 1 (T1) to post-intervention, while scores in the control condition will remain the same from baseline (T1) to T2, week 11. We predict that parents in the delayed treatment group will demonstrate consistent scores on T1, T2 and T3 (re-assessment, prior to delivery of delayed intervention) will remain the same, but that parents will demonstrate higher scores on T4 after receiving the delayed intervention.

Family Empowerment Scale (FES). We will examine change in parent empowerment from baseline (T1) to post-treatment (T2, week 11) in the treatment condition relative to the control condition. Parent empowerment will be measured using the FES. While the study is likely not powered to detect significant differences, our goal is to estimate effect sizes. We predict that parent scores in the treatment group, relative to the control group, will increase from baseline to Time 1 (T1) to post-intervention, while scores in the control condition will remain the same from baseline (T1) to T2, week 11. We predict that parents in the delayed treatment group will demonstrate consistent scores on T1, T2 and T3 (re-assessment, prior to delivery of delayed intervention) will remain the same, but that parents will demonstrate higher scores on T4 after receiving the delayed intervention.

Secondary Outcomes.

PROMIS Parent Proxy Pediatric Anxiety Short Form 8a (P-P Anxiety). We will examine change in child anxiety symptoms from baseline (T1) to post-treatment (T2, week 11) in the treatment condition relative to the control condition. Child symptoms will be measured using the PROMIS P-P Anxiety. While the study is likely not powered to detect significant differences, our goal is to estimate effect sizes. We predict that child scores in the treatment group, relative to the control group, will decrease from baseline to Time 1 (T1) to post-intervention, while scores in the control condition will remain the same from baseline (T1) to T2, week 11. We predict that children of parents in the delayed treatment group will demonstrate consistent scores on T1, T2 and T3 (re-assessment, prior to delivery of delayed intervention) will remain the same, but that these children will demonstrate lower scores on T4 after parents receive the delayed intervention.

PROMIS Parent Proxy Pediatric Depressive Symptoms Short Form 8a (P-P Depression). We will examine change in child depressive symptoms from baseline (T1) to post-treatment (T2, week 11) in the treatment condition relative to the control condition. Child symptoms will be measured using the PROMIS P-P Depression. While the study is likely not powered to detect significant differences, our goal is to estimate effect sizes. We predict that child scores in the treatment group, relative to the control group, will decrease from baseline to Time 1 (T1) to post-intervention, while scores in the control condition will remain the same from baseline (T1) to T2, week 11. We predict that children of parents in the delayed treatment group will demonstrate consistent scores on T1, T2 and T3 (re-assessment, prior to delivery of delayed intervention)

will remain the same, but that these children will demonstrate lower scores on T4 after parents receive the delayed intervention.

Pediatric Symptom Checklist-17 (PSC-17). We will examine change in child internalizing, externalizing, and attention symptoms from baseline (T1) to post-treatment (T2, week 11) in the treatment condition relative to the control condition. Child symptoms will be measured using the PSC-17. While the study is likely not powered to detect significant differences, our goal is to estimate effect sizes. We predict that child scores in the treatment group, relative to the control group, will decrease from baseline to Time 1 (T1) to post-intervention, while scores in the control condition will remain the same from baseline (T1) to T2, week 11. We predict that children of parents in the delayed treatment group will demonstrate consistent scores on T1, T2 and T3 (re-assessment, prior to delivery of delayed intervention) will remain the same, but that these children will demonstrate lower scores on T4 after parents receive the delayed intervention.

Barriers to Treatment Participation Scale (BTPS). We will examine change in parent perceptions of barriers to treatment participation from baseline (T1) to post-treatment (T2, week 11) in the treatment condition relative to the control condition. Barriers to treatment will be measured using the BTPS. While the study is likely not powered to detect significant differences, our goal is to estimate effect sizes. We predict that parent scores in the treatment group, relative to the control group, will decrease from baseline to Time 1 (T1) to post-intervention – indicating a reduction in barriers to treatment, while scores in the control condition will remain the same from baseline (T1) to T2, week 11. We predict that parents in the delayed treatment group will demonstrate consistent scores on T1, T2 and T3 (re-assessment, prior to delivery of delayed intervention) will remain the same, but that parents will demonstrate lower scores on T4 after receiving the delayed intervention.

Difficulties in Emotion Regulation Scale (DERS). We will examine change in aspects of parent emotion from baseline (T1) to post-treatment (T2, week 11) in the treatment condition relative to the control condition. Parent emotion regulation will be measured using the DERS. While the study is likely not powered to detect significant differences, our goal is to estimate effect sizes. We predict that total parent scores and subscale scores in the treatment group, relative to the control group, will decrease from baseline to Time 1 (T1) to post-intervention, while scores in the control condition will remain the same from baseline (T1) to T2, week 11. We predict that parents in the delayed treatment group will demonstrate consistent scores on T1, T2 and T3 (re-assessment, prior to delivery of delayed intervention) will remain the same, but that parents will demonstrate lower scores on T4 after receiving the delayed intervention.

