In addition to creating the infrastructure and content necessary to support PROACTIVE Parent, this study ultimately has two aims:

1. Does the PROACTIVE Parent Program improve foster parents' capacity for supporting their youth in care's mental wellbeing?
2. Does the PROACTIVE Parent Program improve youth in cares' mental health symptoms, as reported by the foster parents?

2.0 Enrollment Criteria (who can be in your study and who would not be eligible to participate in your study):

For the needs assessment, eligible participants are foster parents of youth with a special health care need (including disabilities, mental health needs, and/or complex medical needs). Participants must be over the age of 18 and be actively fostering a child through the Illinois Department of Children and Family Services.

For the pilot study, eligible participants are foster parents of youth with identified mental health needs. Foster parents must be over the age of 18 and be actively fostering a child ages 5-13 through a child welfare agency in the United States. All participants will also need to speak English, be a resident of Illinois, and be able to navigate virtual meeting technologies (e.g. Zoom).

3.0 Sample Size:

For our needs assessment, we anticipate that 1000 caregivers involved in the specialized foster care program will complete our survey. Given that over 3000 caregivers foster youth in care with special health care needs, we believe that this is a feasible number with recruitment support from DCFS.

For our initial pilot study, we will be recruiting 50 caregivers who will receive the pilot intervention. This pilot data will be used to inform a larger iteration of the study, but we believe that 50 caregivers is sufficient for our initial pilot.

4.0 Recruitment and Screening Methods:

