At the same time, the research team will pilot the initial iteration of the PROACTIVE parent model with foster parents of youth in the foster care programs. After foster parents complete an initial screening via REDCap survey, a member of the research team will contact the foster parent to confirm eligibility. The research team member will then obtain informed consent. After consent has been given, the foster parents will be asked to complete an initial and final assessment. Initial assessment is completed prior to attendance of parent coach sessions and the final assessment is completed after the last session.

The subjects will complete a demographics questionnaire (i.e. name, age, sex, gender, race, ethnicity, education, employment, socioeconomic status, address (for mailing payment, confirmation of state residency, and mailing consent form if requested), caseworker contact information) as part of their initial assessment. We will also ask subjects questions regarding their own parenting needs, their youth's mental health needs, and the parents' ability for engaging with mental health services.

During this initial and final assessment, the parent will complete the following measures:

- Parent-Patient Activation Measure – Mental Health
- PROMIS Parent Proxy Measure – Anxiety
- PROMIS Parent Proxy Measure – Depression
- Pediatric Symptom Checklist-17 (Parent Proxy)
- Barriers to Treatment Participation Scale
- Client Satisfaction Questionnaire (final assessment only)

Data will be collected through a REDCap survey.

Parent involvement in the intervention is anticipated to be 30-60 minutes each session (up to 10 sessions) which may occur over the course of up to 12 weeks.

Foster parents will be compensated \$20 after completing the initial assessment *and* attending the initial session. Foster parents will also be compensated \$20 after completing the final assessment. In addition, foster parents will have the ability to earn

continuing education credits necessary for foster parent licensure for completing this program.

Following the initial assessment, the caregiver will meet with a parent coach, who is an internal member of the NU research team, for 30-60 minutes each session. The content of the sessions will consist of one or more of the following:

- 1) introducing the program
- 2) identifying and setting goals
- 3) discussing results of the assessment
- 4) helping parents develop literacy regarding their child(ren)'s mental health needs

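### The protocol describes 50 parents on a single pre/post schedule and the SAP 14 parents in two conditions, so the SAP's Treatment vs. Control analyses cannot be estimated on the study the protocol describes

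*SAP*

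**What the plan says.** **SAP (dated 6/16/21), Statistical Plan.** "We plan to enroll 14 foster parents with 7 foster parents per condition". The primary between-group analysis is a 2 (Group) x 2 (Time) repeated measures ANOVA, or MANOVA for subscales and child outcomes, from T1 to T2. T2 is placed at week 11. A second analysis pools the two conditions, taking T1/T2 from the treatment group and T3/T4 from the delayed group. Each of seven standardized measures carries a hypothesis of change relative to control: P-PAM-MH, FES, PROMIS Anxiety, PROMIS Depression, PSC-17, BTPS and DERS. The first two come under primary outcomes. The SAP concedes that power is probably inadequate and gives effect-size estimation as its goal.

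**Protocol (version 12/08/2021).**
- Section 1.0: both aims begin "Does the PROACTIVE Parent Program improve".
- Section 3.0: "we will be recruiting 50 caregivers who will receive the pilot intervention".
- Section 8.0, assessments: after consent, "the foster parents will be asked to complete an initial and final assessment", and "the final assessment is completed after the last session".
- Section 8.0, start of coaching: "Following the initial assessment, the caregiver will meet with a parent coach".
- Section 8.0, duration: up to 10 sessions, "which may occur over the course of up to 12 weeks".
- Section 8.0, instruments: the list opening "During this initial and final assessment, the parent will complete the following measures" contains neither the FES nor the DERS.
- Section 14.0: two payments of $20, $40 in all, tied to the initial assessment plus first session and to the final assessment.

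The protocol mentions no control condition, allocation, waiting period, T3 or T4. Neither document says how parents would be assigned to conditions.

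**The concern.** The two documents differ in sample size, number of groups, number of assessments and instruments. If the pilot runs as the protocol describes, the SAP's between-group model has no control level to compare with. Both aims ask whether the program improves something, and they would then rest on uncontrolled pre-post change. Such change cannot be separated from time trends or, for child symptoms, from possible regression to the mean in youth selected for identified mental health needs. Section 3.0 says the pilot data will inform a larger study, so a reader needs to know whether a reported effect size is controlled or uncontrolled. FES and DERS results would be promised in the SAP without any listed collection of the data.

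**Working it through.** **1. The SAP's own figure.** 2 conditions x 7 = 14, so the SAP is internally consistent. Against the protocol, 50 - 14 = 36 parents and 50/14 = 3.6. Neither number comes from a power or precision calculation, so there is none to reproduce.

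**2. Designs side by side.**

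| Item | Protocol | SAP |
|---|---|---|
| Date | 12/08/2021 | 6/16/21 (175 days earlier) |
| Parents | 50 | 14 |
| Conditions | none described | 2, with 7 each |
| Assessments | initial, final | T1, T2; also T3, T4 for the delayed group |
| Post-intervention time | after the last session, course up to 12 weeks | T2, week 11 |
| FES, DERS | not listed | analysed (FES under primary outcomes) |

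**3. Estimability.** In a 2 x 2 repeated measures ANOVA, the Group x Time test is equivalent to the group term in a model for the change score (intercept plus group).
- 7 vs 7: the design matrix has rank 2, and the contrast has 1 and 14 - 2 = 12 df.
- 50 parents all on the one treated schedule: the group column duplicates the intercept and the rank is 1. The contrast has 0 df and cannot be estimated. Only mean pre-post change remains, with 50 - 1 = 49 error df.

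The obstacle is the absent control group and absent T3/T4 data, not the number 50. Fifty parents in two conditions would make the contrast estimable.

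**4. Precision.** Estimation is the SAP's stated goal, so the relevant figure is the width of the interval. My assumptions are a two-sided 95% t-interval, equal SD of change in both groups and no dropout. Units are SDs of the change score.

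Between-group difference, half-width = t(0.975, n1+n2-2) x sqrt(1/n1 + 1/n2):
- 7 + 7: 2.179 x 0.5345 = 1.16
- 25 + 25 (hypothetical; neither document proposes this split): 2.011 x 0.2828 = 0.57

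Single-group change, half-width = t(0.975, n-1)/sqrt(n):
- 50 parents: 2.010/7.071 = 0.28
- 14 parents (the SAP's pooled pre-post analysis): 2.160/3.742 = 0.58

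To convert to baseline SDs, multiply by sqrt(2(1-r)), where r is the pre-post correlation. The documents give no value. For an assumed r of 0.5 to 0.8 the factor runs from 1.000 to 0.632:
- 7 + 7: 1.16 to 0.74
- 25 + 25: 0.57 to 0.36
- 50, single group: 0.28 to 0.18

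The between-group and single-group figures belong to different estimands, so 0.28 is not a more precise version of 1.16. The like-for-like pre-post comparison is 0.58 with 14 parents against 0.28 with 50.

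**5. Reach.** All 7 of the 7 standardized measures lose their comparator. Two of the 7, one of them primary, are not in the protocol's list.

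**6. Timing of T2.** A parent whose course runs past week 11, which the protocol permits, would reach the SAP's T2 before finishing. The protocol would assess that parent only afterwards.

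**The case against.** - **The protocol never says single-arm.** In a delayed-treatment design every parent is eventually treated, so the sentence about 50 caregivers does not by itself exclude a waitlist. This is correct, and one group is an inference. It rests on the two-assessment schedule, coaching following the initial assessment, the two payments, and silence on control, assignment and T3/T4. If a waitlist is intended, the protocol omits it, and that needs correcting just as much.
- **The SAP may simply be out of date.** It may be, and the repair could then be an SAP update alone. But neither document says the SAP is superseded, and no later analysis plan is supplied.
- **The impact is limited.** Acceptability, utility and feasibility are primary, are analysed descriptively and need no control. A one-way pre-post analysis of the measures that are collected also remains possible. This stands, but P-PAM-MH and FES are also under primary outcomes, and the SAP attaches a control comparison to both.
- **The T2 point is minor.** Twelve weeks is a maximum, and if the 10 sessions were weekly, week 11 would follow the last one. The conflict therefore affects only longer courses. It is less serious than 14 against 50, but one definition is still needed.

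**Conclusion.** The concern holds and must be fixed. On the single-group schedule the protocol describes, the SAP's Group x Time effect has 0 df, and none of its 7 standardized measures has a comparator. FES and DERS would not be collected as section 8.0 is written. The half-widths (1.16 for 7 vs 7, 0.28 for single-group change in 50) depend on the assumptions of equal SDs and no dropout; the loss of the contrast does not. It depends only on reading the protocol as one group, which its schedule strongly supports. The descriptive primary outcomes are untouched. Confidence is high.

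**What to change.** State one design in both documents.

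**(a) If single-arm:** in the SAP, replace the 14 parents and two conditions with 50 parents. Delete the Group x Time and delayed-treatment analyses, and specify a one-way pre-post analysis with 95% confidence intervals. Restate both aims as estimating uncontrolled change. The cost is an SAP revision, a change to the wording of the protocol's aims, and the loss of any control contrast.

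**(b) If delayed-start:** write into the protocol the two conditions, the number in each, the method of assignment (if random, how the list is generated and concealed), T1 to T4 and the related compensation. Set one calendar-anchored T2 for both arms, no earlier than the end of the permitted course, and carry the same numbers into the SAP. Delayed parents then wait and complete extra online assessments, with any payments attached. Section 11.0 has consent explain how the intervention is structured, so the consent material would need revising too.

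**In either case:** use one definition of the post-intervention assessment, and either add FES and DERS to protocol section 8.0 or remove them from the SAP. Adding them lengthens each assessment.
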